6.5 SAFETY ANALYSES

Safety will be assessed through summaries of adverse events, changes in laboratory test results, changes in vital signs and ECGs, and exposure to study drugs. Exposure to combination treatment and length of safety follow-up will be summarized by treatment arm within each stage.

All verbatim adverse event terms will be mapped to Medical Dictionary for Regulatory Activities thesaurus terms, and adverse event severity will be graded according to NCI CTCAE v5.0, and severity of CRS will also be graded by the investigator according to the ASTCT Consensus Grading (Lee et al. 2019). All adverse events, serious adverse events, adverse events leading to death, adverse events of special interest, and adverse events leading to study treatment discontinuation that occur on or after the first dose of study treatment (i.e., treatment-emergent adverse events) will be summarized by mapped term, appropriate thesaurus level, and severity grade. For events of varying severity, the highest grade will be used in the summaries. Deaths and causes of death will be summarized.

Relevant laboratory, vital sign (pulse rate, respiratory rate, blood pressure, pulse oximetry, and temperature), and ECG data will be displayed by time, with grades identified where appropriate. Additionally, a shift table of selected laboratory tests will be used to summarize the baseline and maximum postbaseline severity grade. Changes in vital signs and ECGs will be summarized.

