2. OBJECTIVES AND ENDPOINTS

This study will evaluate the efficacy, safety, and pharmacokinetics of multiple treatment combinations in patients with advanced GC or GEJC. Specific objectives and corresponding endpoints for the study are outlined below for Stage 1 (see Table 2) and Stage 2 (see Table 3).

Table 2 Objectives and Corresponding Endpoints for Stage 1

Primary Efficacy Objective	Corresponding Endpoint

 To evaluate the efficacy of treatment combinations during Stage 1 	
 ORR, defined as the proportion of patients with a complete response or a partial response on two consecutive occasions ≥ 4 weeks apart during Stage 1, as determined by the investigator according to RECIST v1.1
Secondary Efficacy Objective	Corresponding Endpoints

 To evaluate the efficacy of treatment combinations during Stage 1 	
 PFS after randomization, defined as the time from randomization to the first occurrence of disease progression or death from any cause (whichever occurs first) in Stage 1, as determined by the investigator according to RECIST v1.1 OS after randomization, defined as the time from randomization to death from any cause, regardless of stage OS at specific timepoints (e.g., 6 and 12 months) DOR, defined as the time from the first occurrence of a documented objective response to disease progression or death from any cause (whichever occurs first) in Stage 1, as determined by the investigator according to RECIST v1.1 Disease control rate, defined as the proportion of patients with stable disease for ≥ 12 weeks or a complete or a partial response, as determined by the investigator according to RECIST v1.1
Safety Objective	Corresponding Endpoint

 To evaluate the safety of treatment combinations during Stage 1 	
 Incidence and severity of adverse events, with severity of all events graded according to NCI CTCAE v5.0 and severity for CRS also graded according to the ASTCT CRS Consensus Grading Scale

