- ^b If clinical activity is observed in an experimental arm during the preliminary phase, approximately 25 additional patients may be enrolled in that arm during the expansion phase. Experimental arms with minimal clinical activity or unacceptable toxicity will not undergo expansion.
- ^c The treatment regimen in the control arm may change with emerging data to reflect the evolving standard-of-care treatments, and new control arm treatment will be updated by amending the protocol.
- ^d The randomization ratio will depend on the number of experimental arms that are open for enrollment (e.g., if an arm is added or enrollment in an arm is suspended pending analysis of results from the preliminary phase), with the stipulation that the likelihood of being allocated to the control arm will be no more than 50% (see Section 3.1.2 for details).

Figure 2 Detailed Study Design

Atezo = atezolizumab; CAPOX = capecitabine plus oxaliplatin; GC = gastric carcinoma; GEJC = gastroesophageal junction carcinoma; R = randomization; Tira = tiragolumab.

^a Patients who experience loss of clinical benefit as determined by the investigator (details provided below) or unacceptable toxicity during Stage 1 may be eligible to receive a different treatment combination during Stage 2, provided they meet the eligibility criteria and a Stage 2 arm is open for enrollment. Details are provided in the respective appendix for each treatment arm (see [Appendix 7](#) and [Appendix 8](#)).

Patients in the control and experimental arms will continue to receive treatment until unacceptable toxicity or loss of clinical benefit as determined by the investigator after an integrated assessment of radiographic and biochemical data, local biopsy results (if available), and clinical status (e.g., symptomatic deterioration such as pain secondary to disease).

Because of the possibility of an initial increase in tumor burden caused by immune cell infiltration in the setting of a T-cell response (termed pseudoprogression) with atezolizumab and other CITs, radiographic progression per Response Evaluation Criteria in Solid Tumors, Version 1.1 (RECIST v1.1) may not be indicative of true disease progression. In the absence of unacceptable toxicity, patients who meet criteria for disease progression per RECIST v1.1 while receiving treatment with a CIT-based combination will be permitted to continue treatment if they meet all of the following criteria:

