5.3.1 Adverse Event Reporting Period

Investigators will seek information on adverse events at each patient contact. All adverse events, whether reported by the patient or noted by study personnel, will be recorded in the patient's medical record and on the Adverse Event eCRF.

After informed consent has been obtained but prior to initiation of study treatment, only serious adverse events caused by a protocol-mandated intervention (e.g., invasive procedures such as biopsies, discontinuation of medications) should be reported (see Section 5.4.2 for instructions for reporting serious adverse events).

After initiation of study treatment, all adverse events will be reported until 30 days after the final dose of study treatment or until initiation of new systemic anti-cancer therapy, whichever occurs first, and serious adverse events and adverse events of special interest will continue to be reported until ■■■ days after the final dose of study treatment or until initiation of new systemic anti-cancer therapy, whichever occurs first.

Instructions for reporting adverse events that occur after the adverse event reporting period are provided in Section 5.6.

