6. STATISTICAL CONSIDERATIONS AND ANALYSIS PLAN

The final study analysis will be based on patient data collected through study discontinuation. If not otherwise specified, efficacy analyses will be based on the efficacy-evaluable population, defined as all patients who receive at least one dose of each drug for their assigned treatment regimen, and safety analyses will be based on the safety-evaluable population, defined as all patients who receive any amount of study treatment.

The analysis results will be summarized by the treatment regimen that patients actually receive, as well as by stage (Stage 1 or Stage 2). Data will be described and summarized as warranted by sample size. Continuous variables will be summarized through use of means, standard deviations, medians, and ranges. Categorical variables will be summarized through use of counts and percentages. Listings will be used in lieu of tables in the event of small sample sizes.

New baseline values will be established for the Stage 2 efficacy and safety analyses. For evaluation of tumor response, new baseline tumor assessments will be established as described in Section 4.5.6. For other endpoints (e.g., change from baseline in vital signs or laboratory test results), the last non-missing value prior to a patient's first dose during Stage 2 will serve as the new baseline.

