Appendix 7: Study Details Specific to Atezo + CAPOX Arm (Control) (cont.)

The acceptable length of treatment interruption must be based on the investigator's benefit–risk assessment and in alignment with the protocol requirements for the duration of treatment and documented by the investigator. The Medical Monitor is available to advise as needed.

A7–4.1.2.2 CAPOX

Treatment will be administered as follows during each 21-day cycle for up to 6 cycles:

- Capecitabine (1000 mg/m²) orally twice a day on Days 1–14
- Oxaliplatin (130 mg/m²) by IV infusion on Day 1 at least 5 minutes after completion of the atezolizumab infusion

The rates of drug administration for oxaliplatin may follow the institutional guidelines. Patients may be premedicated with 5-HT₃–receptor antagonists or other standard-of-care methods to control nausea and vomiting. Premedication with steroids should be limited when clinically feasible, because of their immunosuppressant effects. All medications must be recorded on the appropriate Concomitant Medications eCRF.

Guidelines for dosage modification and treatment interruption or discontinuation because of toxicities are provided in Section [A7–5.1.4](#). CAPOX treatment may be interrupted for reasons other than toxicity (e.g., surgical procedures). The acceptable length of treatment interruption must be based on the investigator's benefit–risk assessment and in alignment with the protocol requirements for the duration of treatment and documented by the investigator. The Medical Monitor is available to advise as needed.

A7–4.2 CONCOMITANT THERAPY FOR ATEZO + CAPOX ARM

Concomitant therapy consists of any medication (e.g., prescription drugs, over-the-counter drugs, vaccines, herbal or homeopathic remedies, nutritional supplements) used by a patient in addition to protocol-mandated study treatment from 7 days prior to initiation of study treatment to the treatment discontinuation visit. All such medications should be reported to the investigator and recorded on the Concomitant Medications eCRF.

A7–4.2.1 Permitted Therapy for Atezo + CAPOX Arm

Patients are permitted to use the following therapies during the study:

- Oral contraceptives with a failure rate of < 1% per year
- Hormone-replacement therapy
- Prophylactic or therapeutic anticoagulation therapy
- Vaccinations (such as influenza, COVID-19)
 - Live, attenuated vaccines are not permitted (see [A7–4.2.3](#)).
- Megestrol acetate administered as an appetite stimulant

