Appendix 8: Study Details Specific to Atezo + CAPOX + Tira Arm (cont.)

the placebo plus atezolizumab arm (n=29; 17.2% [95% CI: 1.8% to 32.7%]). Of note, responders in the tiragolumab plus atezolizumab arm included patients with both squamous and non-squamous histology.

In the ITT population, investigator-assessed PFS was improved in the tiragolumab plus atezolizumab arm compared with the placebo plus atezolizumab arm (stratified HR: 0.57 [95% CI: 0.37 to 0.90]; median PFS: 5.4 vs. 3.6 months, respectively). In the subgroup of patients with TPS \geq 50%, investigator-assessed PFS was improved in the tiragolumab plus atezolizumab arm compared with the placebo plus atezolizumab arm (unstratified HR: 0.33 [95% CI: 0.15 to 0.72]; median PFS: not estimable vs. 3.9 months, respectively).

As of the data cutoff date, most adverse events have been Grade 1 or Grade 2. Serious adverse events, Grade 3–5 adverse events, adverse events leading to discontinuation, and adverse events leading to death have been balanced between the two treatment arms. Serious and high-grade treatment-related adverse events have also been balanced between the two treatment arms. [REDACTED] have been balanced between the two treatment arms, with the exception of a higher frequency of infusion-related reaction (IRR) and rash reported in the atezolizumab plus tiragolumab arm.

[REDACTED]

Overall, tiragolumab in combination with atezolizumab has been well tolerated, adverse events have been manageable, and the safety profile seems to be consistent as reported across different solid tumor indications.

Refer to the Tiragolumab Investigator's Brochure for additional details on all ongoing and planned clinical studies.

A8–2.7 BENEFIT–RISK ASSESSMENT

Taking into account the potentially synergistic mechanisms of action of tiragolumab and atezolizumab, as well as the preliminary efficacy and manageable safety profiles of the above-described combinations, treatment with atezolizumab, CAPOX, and tiragolumab (Atezo + CAPOX + Tira) may have therapeutic potential in solid tumors such as GC and GEJC.

For the evaluation of the impact of the (coronavirus disease 2019) COVID-19 pandemic on the benefit–risk assessment, please refer to Section 1.4.

**A8–3 RATIONALE FOR DOSE AND SCHEDULE FOR
ATEZO+CAPOX+TIRA ARM**

[figure not shown]
A8–3.1 RATIONALE FOR ATEZOLIZUMAB DOSE AND SCHEDULE

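### If treatment duration differs between arms, crude adverse-event percentages will mix event rate with observation time; exposure-adjusted and fixed-window summaries are a cheap addition

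*Combined protocol and SAP*

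**What the plan says.** The Stage 1 safety endpoint in Section 2 is "Incidence and severity of adverse events, with severity of all events graded according to NCI CTCAE v5.0". Section 6.5 states that treatment-emergent events "will be summarized by mapped term, appropriate thesaurus level, and severity grade". That sentence does not name the statistic; it comes from the general rule in Section 6: "Categorical variables will be summarized through use of counts and percentages". Read together, they plan crude proportions by arm. The visible text contains no person-time rate, time to first event or fixed-window summary.

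Section 5.3.1 sets the window: "all adverse events will be reported until 30 days after the final dose of study treatment or until initiation of new systemic anti-cancer therapy", whichever comes first. Serious and special-interest events are collected for longer, with the day count redacted. Section 3.1.2 makes treatment open-ended: "Patients in the control and experimental arms will continue to receive treatment until unacceptable toxicity or loss of clinical benefit as determined by the investigator". Only the chemotherapy is capped (Appendix 7, A7-4.1.2.2, with the same cap in Appendix 8): "Treatment will be administered as follows during each 21-day cycle for up to 6 cycles".

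Section 6.5 also summarises exposure and length of safety follow-up by arm, and events that lead to stopping treatment. Section 6.2 tabulates the reasons for stopping. None of these enters the event summaries as a denominator.

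**The concern.** How long a patient is observed for adverse events depends on how long that patient stays on treatment, so the window is itself an outcome of the arm. Appendix 8 (A8-2.4) hypothesises more durable benefit with tiragolumab. If that happens, its patients are watched for longer and more of them will have had at least one event, even at an unchanged event rate. If toxicity shortens treatment, the reverse occurs and harm looks smaller.

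The events most exposed to this are those that keep accruing on the antibodies after CAPOX ends. Section 1.3 includes a control arm to strengthen signal detection, so readers will set the two columns of percentages side by side. At stake is whether they read a difference in observation time as a difference in toxicity.

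**Working it through.** **The plan's own figure.** The documents give no event rate, exposure or safety precision to reproduce. The sample size does reproduce: at an assumed 1:1 ratio (control share is capped at 50%), 2 × 20 = 40 and 2 × (20 + 25) = 90, matching the stated 40–90. Arms of 20 and 45 are used below.

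**Inputs.**
- Control median treatment time: 7 months, an assumption. Appendix 7 (A7-1.2) quotes a CAPOX median PFS of about 6–7 months. Using 6 or 7.7 months changes the results by at most 0.2 points.
- Duration ratio (control median ÷ experimental median): 0.57, the PFS hazard ratio in the NSCLC study of A8-2.6.2; 0.74, the nivolumab-plus-chemotherapy PFS hazard ratio at CPS ≥ 5 in Section 1.2; and 0.85 and 1.25, assumed.
- Event rate λ: constant and equal in both arms, an assumption, set so that the control percentage is 10, 20, 40 or 60%.
- Window: treatment time plus w = 30 days (0.99 month), with exponential treatment time at rate μ = ln 2 ÷ median.

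**Formula 1.** P(at least one event) = 1 − e^(−λw) · μ/(μ + λ).

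**Worked case** (control 40%, ratio 0.57). Control: μ = 0.693/7 = 0.0990 and λ = 0.0570 per month, so 1 − 0.9454 × 0.6347 = 0.400. Experimental: median 7/0.57 = 12.3 months and μ = 0.0564, so 1 − 0.9454 × 0.4975 = 0.530. The false excess is 13.0 points.

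False difference in points, experimental minus control, control median 7 months:

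| Duration ratio (exp. median) | Control 10% | 20% | 40% | 60% |
|---|---|---|---|---|
| 0.57 (12.3 mo) | +5.8 | +9.7 | +13.0 | +11.7 |
| 0.74 (9.5 mo) | +2.8 | +4.8 | +6.8 | +6.5 |
| 0.85 (8.2 mo) | +1.4 | +2.5 | +3.6 | +3.5 |
| 1.00 (7.0 mo) | 0 | 0 | 0 | 0 |
| 1.25 (5.6 mo) | −1.7 | −3.0 | −4.7 | −4.9 |

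Using the NSCLC medians directly ("median PFS: 5.4 vs. 3.6 months, respectively"), a one-month tail and rates of 0.03–0.05 per month gives 16.0–24.5% against 21.3–31.5%, an excess of 5–7 points.

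**Events confined to the six CAPOX cycles** (6 × 21 = 126 days, hazard zero afterwards). Formula 2, for a first event by time t: 1 − e^(−λw) + e^(−λw) · λ/(λ + μ) · [1 − e^(−(λ+μ)(t−w))]. With control at 20, 40 and 60%, the longer-treated arm shows 20.9, 41.7 and 62.2% at ratio 0.57, and 20.5, 41.0 and 61.3% at ratio 0.74. The excess is 0.5 to 2.2 points.

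**Early data cut.** If each patient's follow-up is capped at 6 months (an assumption), with rates of 0.03–0.05 per month, the excess is 1.3–2.0 points for medians 3.6/5.4, 1.0–1.6 for 7.7/13.5 (7.7/0.57) and 0.5–0.7 for 7.7/9.6 (7.7/0.8, an assumed ratio).

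**Sampling error.** The Wald 95% half-width is 1.96 × √[(p₁q₁ + p₂q₂)/n]. For 40% against 53%, p₁q₁ + p₂q₂ = 0.489, giving 20.4 points at n = 45 and 30.7 at n = 20. Across the scenarios with longer experimental treatment it is about 13–20 points at 45 per arm and 19–31 at 20. The false difference is smaller in every case; at its largest it is 13.0/20.4, about two thirds of the half-width.

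**Check of the fix.** In the worked case, a simulation of 2 million patients per arm gave first events per person-month of 0.0570 in both arms, a ratio of 1.00. Formula 2 at Week 18 gives 18.9% against 19.8%, leaving 0.9 points of the original 13.0. Over the three pairs of medians above, at 0.03–0.05 per month, the residue is 0.2–1.0 points at Week 18 and 0.5–2.0 at Month 6.

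**The case against.** The strongest reply is that this is a descriptive study. Section 6.1 disclaims power and type I error considerations, and Section 6.4.1 plans a between-arm difference for ORR only. A reader might infer that the safety comparison is already biased; the documents do not support that. No safety contrast is specified, and any distortion needs unequal durations, which are unknown in advance. This objection stands.

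Section 6.5 also shows exposure and follow-up beside the event tables, and the discontinuation tables would reveal a toxic arm that stops early. This stands in part. Summary exposure tells a reader that an imbalance exists, but does not allow time at risk for a first event to be rebuilt for each term and grade.

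A reader might further infer that crude percentages will drive decisions to close or expand the arm. Section 3.1.5 has the Internal Monitoring Committee weigh all available data, Section 6.9 is redacted, and early reviews would see truncated follow-up. That link is not shown.

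Finally, the sizes rest on borrowed figures: an NSCLC hazard ratio from a study without chemotherapy, and a biomarker subgroup on another drug. PFS is only a proxy for treatment time, since Section 3.1.2 allows treatment past RECIST progression. (The synopsis instead ties the end of treatment to RECIST progression; the two passages must be reconciled because they imply different windows.) The 30-day tail does not describe serious or special-interest events, whose longer window is redacted. All of this limits the numbers but leaves the mechanism intact.

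**Conclusion.** The concern holds as a conditional one. As written, the plan reports crude percentages over a window that follows treatment duration, without adjustment. If durations differ, the percentages overstate harm in the longer-treated arm and understate it in the shorter-treated one; if they do not differ, there is no distortion.

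Under equal constant event rates and the proxies above, the false difference is about 3 to 13 points for steadily accruing events at duration ratios of 0.74 to 0.57, and 1.4 to 3.6 at 0.85. It is about 0.5 to 2 points for events tied to the CAPOX cycles, and 2 points or less at a 6-month cut. These are illustrations, not forecasts, and all lie within sampling error at 20 to 45 per arm. More patients would narrow the interval without removing the artefact.

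The practical risk is misreading of descriptive tables, mainly for events that continue on antibody treatment after CAPOX. This is a cheap improvement and not a flaw in a planned inference.

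**What to change.** Keep the crude tables. In Section 6.5 add, by arm, for all-grade, Grade 3 or higher, serious and special-interest events:

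- (a) patients with a first event per 100 patient-months at risk within the reporting window that applies to that category, with a 95% CI;
- (b) a fixed-window summary, such as cumulative incidence of first event by Week 18 (the nominal end of six CAPOX cycles), with death and end of the window as competing events.

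State that any between-arm difference in crude percentages is to be interpreted together with (a) and (b). They should not replace the crude tables as the sole basis for between-arm statements: (a) assumes a roughly constant hazard, and (b) leaves a small residue because the arms can still differ in time spent within the window.

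The cost is a few sentences and a few extra tables from dates already collected, with no change to treatment or visits. Both measures will be imprecise at this sample size.

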6.6 PHARMACOKINETIC ANALYSES

Sparse samples will be collected for potential PK analyses of atezolizumab (patients who receive at least one dose of atezolizumab) and specified drugs given in combination with atezolizumab (patients who receive at least one dose of the drug). Serum or plasma concentrations of the various study drugs may be reported as individual values and summarized (mean, standard deviation, coefficient of variation, median, range, geometric mean, and geometric mean coefficient of variation) by treatment arm, and by cycle and day when appropriate and as data allow. Individual and median serum or plasma concentrations of the various study drugs may be plotted by treatment arm, cycle, and day when appropriate and as data allow. PK data for combination drugs may be compared with available historical data from internal and published previous studies. Atezolizumab or other study drug concentration data may be pooled with data from other studies using an established population PK model to derive PK parameters such as clearance, volume of distribution, and area under the concentration–time curve.

